 - If the family member is literally relaying a surgeon's questions to a patient, or even relaying but also adding their own content beyond what the surgeon asked, do not count this as a question
 - If the family member is relaying a patient or another family member's question to the surgeon, do count this as question, as the question will separately be coded/collected as shown in #2 above
 - If a family member acting as an interpreter asks their own question to the surgeon, this is coded/collected as any other family member question would be

Step 2: Who said it? Determine the speaker

- Code all questions asked by patients or family members/loved ones while surgeon is in the room
- Do not distinguish between family members – these are all coded as “family member”
 - In some cases, a support person such as a friend may be present. Code their questions as “family member” as well
- If question speaker is unknown, count these as patient questions UNLESS transcriptionist makes a note it's a medical provider (though they are unsure of *which* provider) AND the content of the question indicates that a clinician asked it
- Do not code questions asked by the surgeon, resident(s), or other clinical staff
- Exclude questions asked while the surgeon is not present

Step 3: Code the topic area

Look for content before and after the question to determine its topic area/context. However, do not exclusively base your topic coding on how the surgeon answers the question – it is possible the surgeon may have misinterpreted the question or even ignored it. However, if the conversation seems to be consistently in one line of thought, the surgeon's response may help clue you into what the topic area should be coded as. What the patient says immediately before/after the question may also be helpful if you are struggling to identify the topic area. You may only code each question as having one topic area so carefully review the topic area codes to determine which best fits the question.

There are 6 topic area codes: OPTIONS, EXPECTATIONS, LOGISTICS AND TECHNICAL CONCERNS, RISKS/COMPLICATIONS, ADVANCE DIRECTIVES, OTHER. These are each described in more detail below. But first, here is some guidance on how to handle very short questions.

How should I code the topic area for very short questions?

- Short questions that stand all alone without any text surrounding them on that line of the transcript are always coded as “OTHER” and count as a single question. Examples:

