 - “Is that right?”
 - “Really?”
 - “Huh?”
 - “Oh did he?”
 - “You know what I'm saying?”
 - “Oh, yeah?”

- Similarly, short questions that are a reiteration of what was previously said or are purely rhetorical are coded as one question with “OTHER” as the topic area. Examples:
 - “Oh really, two thirds?”
 - “It does, doesn’t it?”
 - “Now what was I going to say?”
 - *Surgeon*: “I’ve trained since 1984, so. So if you, we all do about 200 to 250 operations, 200 to 250 operations a year.”
Patient: “Wow. Since ’84?”
- If a patient or family member asks the same question twice or more with the exact same wording, code the first instance of the question based on its content and code the second/any later instances as “OTHER”. Example:
 - *Patient*: Rehab for 6 weeks? [this would be coded as “EXPECTATIONS”]
 - *Surgeon*: Yeah.
 - *Family member*: Rehab for 6 weeks? [this would be coded as “OTHER”]
 The question must be exactly the same for this rule to apply. If there are minor wording changes, code each question as you would normally. Example:
 - *Patient*: Rehab for 6 weeks? [this would be coded as “EXPECTATIONS”]
 - *Surgeon*: Yeah.
 - *Family member*: ‘He’d be in rehab for 6 weeks?’ [this would be coded as “EXPECTATIONS”]
- Short questions that are attached or directly next to a statement (in the same line of text) that is substantive (not simply re-stating what has already been said) are coded based upon the topic of the statement that precedes the short question. The short question is considered attached to the longer statement to be coded as ONE question. When filling out the coding sheet, include both the statement and the short question. This applies to short questions that are next to a statement and separated either by a comma OR a period
 - “But it’s inside the aorta, right?”
 - This question should be coded as “LOGISTICS AND TECHNICAL CONCERNS”
 - “But it’s in the aorta. No?”
 - This question should be coded as “LOGISTICS AND TECHNICAL CONCERNS”
 - “There’s no nano-technology on it yet. Right?”
 - This question should be coded as “LOGISTICS AND TECHNICAL CONCERNS”
 - “So this seems like my only option, right?”
 - This question should be coded as “OPTIONS”
- Short questions that are attached or directly next to a substantive question count as two questions ALTHOUGH the topic code for each question may be different. Usually, the short question is coded as “OTHER” while the longer question is coded according to the topic

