 - “So the chances of it opening up again are low? Right?”
 - This is two questions; the first coded as “RISKS/COMPLICATIONS”, the second coded as “OTHER”

OPTIONS

“What can I do for this problem?” or “Are there other treatments apart from surgery?” are the main sentiments behind this topic area. This code should be used for questions that seek to understand what

the different treatment paths or choices are or to compare treatments. Look for words like: options, choices, alternatives

- Use this code for any questions that reference seeking additional information on possible treatment options including
 - Surgery Choice #1 vs Surgery Choice #2
 - Observation vs Surgery (Observation includes non-surgical alternatives like symptom management/medical treatment)
 - Different approaches to surgery:— open, laparoscopic, endoscopic (e.g. with catheters) (see Appendix A for examples of approaches)
 - Radiation vs chemotherapy
- Use this code for questions that are asking for recommendations: What do you think? What would you recommend?
 - Some requests for recommendations may be subtle and may sound like the patient/family member is asking for reassurance regarding a particular treatment choice
 - For example: “So there’s really no point in putting it off, right?” or “So I’m not a gambling man, but that sounds like a reasonable investment, right?”
- This includes questions about having more options if the patient does something (gains weight, stops smoking, tumor shrinks with chemo) or something happens to allow another option to be available: “If I _____, is this treatment possible?”
- Do not code questions as being “OPTIONS” if they’re about options for other things *within* the major treatment (such as whether to get a blood transfusion during surgery, what type of equipment the surgeon will use, or where an incision is made). These would instead be coded under “Logistics and Technical Concerns”
- “OPTIONS” VS “LOGISTICS” – is it about an option or a technique within an option?
 - *What vs. how* is a good way to distinguish between these two topic areas. Questions asking *what are the options* are coded as “OPTIONS” whereas questions on *how to do it* are coded as “LOGISTICS”

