 - If the question is about a treatment *approach* code it as “OPTIONS”. Words that indicate a treatment *approach* is being discussed include: open, minimally invasive, laparoscopic, endoscopic, robotic, endovascular or catheter based approach (includes TAVR/TAVI, EVAR or TEVAR), single incision/single port, or any option that involves interventional radiology instead of surgery
 - However, if a question is about a technique *within* an option, code it as “LOGISTICS”. Techniques include: staples versus stitches/hand sewn, type of stent or catheter, type of graft, and reference to specific equipment/techniques – e.g. lasers, ablation, coagulation devices, ultrasound, ligasure, staplers, fluoro, dilators, scopes, cameras, specific needles or types of sutures
- “OPTIONS” VS. “EXPECTATIONS” OR “RISKS”
 - If a question is *comparing* outcomes/risks/expectations between two or more treatment options, code it as “OPTIONS”. Look for words that indicate the speaker is thinking about the relative value of things (better/worse than)
 - Example: “It’ll give it a better chance?”
 - However, if the question is asking about risks of a procedure, what life will be like within a given treatment, or after a treatment decision has been made, code this as “RISKS” or “EXPECTATIONS”. A question is NOT coded as “OPTIONS” *unless* it seeks to compare two or more options.

- Example: "So I would end up with paralysis if I didn't have the surgery?" [This is coded as OPTIONS because it's focused on *comparing* outcomes between surgery and no surgery]
Example: "How likely is it that I will be paralyzed after surgery? [This is coded as "RISKS" because it is focused on the risks of surgery only]
- "OPTIONS" examples:
 - "What is the difference between the aftereffects of radiation versus chemo as far as...the feeling?"
 - "Is there another way?"
 - "So what alternative do you think would be good?"
 - "If I was your dad, what would your advice be?"
 - "So if I, if I put weight on, and I gain some more weight, that would make a difference?" [asking if they could get a specific surgery if they put weight on]
 - "So this seems like my only option, right?"

LOGISTICS AND TECHNICAL CONCERNs

Questions about how things will work up to and through surgery. Once they hit the post-operative stage, those questions go under "EXPECTATIONS". Use the time period in the question as your guide on when to use this code.

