These discussions generated the first decision support target for our QPL: "Should I have surgery?" Our PFAC wanted patients to deliberate about having surgery and receive explicit information about how surgery might improve symptoms or longevity. To address this need, our stakeholders selected the question prompts:

- "What are my options?"
- "What is likely to happen if I do have surgery? If I don't have surgery?"
- "Will surgery make me feel better?" and
- "Will surgery help me live longer? If so, how much longer?"

Expectations

The PFAC explored qualitative data suggesting patients were unprepared for what occurred postoperatively. For example, 1 patient noted she had been apprised of specific risks, but did not recognize this information could be used to prepare for complications or prolonged recuperation. She described how frightened she was by her slow recovery and postoperative weakness:

No, no I wasn't expecting anything. They didn't tell me there could be [complications]. They did say you could develop A-fib and they did say that after the operation you could have a stroke or heart attack....So I didn't really, I did ask questions, but I guess I didn't ask if it would be a long recovery or what could happen...I mean you're not expecting, and I don't think you know all the questions you should ask.

Although surgeons named risks and described operations under consideration as *big surgery*, patients struggled to translate this information. Patients assumed they would return to normal postoperatively: “If I can’t come back normal, I don’t want to come back.”

The PFAC expressed concern that patients underestimated the impact of surgery and had a naive outlook about the seriousness of surgery, leading to surprise or distress when recovery was arduous. This notion was familiar to PFAC members who reported feeling “blindsided” postoperatively. They worried that what was normal after surgery for the surgeon was not normal for the patient and this might cause distress when the surgeon’s expected outcome was unexpected by the patient.

This discussion generated the target: “What should I expect if everything goes well?” The PFAC chose question prompts to prepare for recovery and long-term physical changes, including:

- “How do you think my daily life will look after surgery? Right after surgery, 3 months later, 1 year later?”
- “Will I have any tubes or drains put in during or after surgery? Will I need them at home?”

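### The coding manual's blanket rule sending short stand-alone questions to OTHER conflicts with its own examples and definitions; it should be limited to content-free utterances and its use checked while coding is blinded

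*Combined protocol and SAP*

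**What the plan says.** The four Aim 1 question endpoints are counts by topic, grouped as 0, 1, 2+ for OPTIONS, EXPECTATIONS and RISKS and as 0, 1+ for ADVANCE DIRECTIVES (SAP, Aim-1 primary outcomes). OTHER and LOGISTICS are not primary categories. The SAP section on data coding has each transcript's questions coded by one coder, and all coding finished before unblinding.

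Step 3 of the Question Coding Manual, before it defines the topics, gives guidance on very short questions. Its first bullet says that "Short questions that stand all alone without any text surrounding them on that line of the transcript are always coded as" OTHER. The six examples that follow are conversational fillers, the longest being "You know what I'm saying".

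Elsewhere the manual says:

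- In the same guidance, under the rule on repeated wording, a patient's line reads "Rehab for 6 weeks? [this would be coded as" EXPECTATIONS.
- The OPTIONS section covers requests for a recommendation, such as "What do you think? What would you recommend", and lists "Is there another way" among its examples. It tells coders: "Look for words like: options, choices, alternatives".
- The OTHER section says that very short questions are *sometimes* coded there, and Step 4 follows a warning not to use the code as a catchall.

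**The concern.** The rule as worded depends on length and on standing alone on a transcript line, not on what is asked. *Short* is not defined, and *always* leaves no room for judgement. A coder who follows the rule and a coder who follows the examples can give the same line different codes, and with one coder per transcript no second reading is planned that would show it.

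The endpoints are sensitive to single lines. One question moved to OTHER can take a visit from 1 to 0, or from 2+ to 1. The first prompt listed in the QPL development paper (Results, Choices), "What are my options", is itself a brief question. If a patient says it as a separate turn, the literal rule and the OPTIONS definition disagree about a behaviour that the intervention is meant to produce.

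**Working it through.** The plan gives no figure for this point, so the main check sets the texts side by side.

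**1. Can a length cut-off reconcile the rule and the examples?**

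| Question | Words | Code in the manual |
|---|---|---|
| "You know what I'm saying" | 5 | OTHER |
| The other five examples under the rule | 3, 1, 1, 3, 2 | OTHER |
| "Rehab for 6 weeks" | 4 | EXPECTATIONS |
| "Is there another way" | 4 | OPTIONS |
| "What do you think? What would you recommend" (two questions) | 4 and 4 | OPTIONS |
| *Which valve?* | 2 | LOGISTICS |

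No cut-off separates the two groups: a five-word question is OTHER, while two-word and four-word questions are coded by topic. Content does separate them. Every OTHER example is empty of topic, and every topic-coded example has one.

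**2. Which examples meet all the conditions of the rule?** The rule needs a short question with nothing else on its line. The rehabilitation question is shown that way, so it is a direct conflict. The OPTIONS and LOGISTICS examples are listed without their transcript lines, so they show only that brevity alone does not lead to OTHER. *Always* against *sometimes* is a further conflict.

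**3. What about the listed prompt?** "What are my options" has four words, fewer than the five-word OTHER example. The OPTIONS section assigns questions asking what the options are to OPTIONS and names that keyword. The prompt is therefore OTHER under one instruction and OPTIONS under another.

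**4. How far could this move an endpoint?** This is an illustration; the documents give no rate of affected lines.

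Inputs from the SAP's updated power section are 65% of control visits with zero questions, so p0 = 0.35, and an odds ratio of 1.3.

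- Intervention odds = (0.35/0.65) × 1.3 = 0.70, so p1 = 0.70/1.70 = 0.412.
- Assume that a share m of the visits with an on-topic question falls to zero, equally in both arms. The observed odds ratio is [p1(1−m)/(1−p1(1−m))] / [p0(1−m)/(1−p0(1−m))].

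| m (assumed) | Control | Intervention | Observed odds ratio |
|---|---|---|---|
| 0 | 0.350 | 0.412 | 1.30 |
| 10% | 0.315 | 0.371 | 1.28 |
| 20% | 0.280 | 0.329 | 1.26 |
| 30% | 0.245 | 0.288 | 1.25 |

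Even with a large equal loss, the odds ratio moves only slightly towards 1.

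**The case against.** The strongest reply is that the rule is clear in context. It sits under guidance on very short questions and all its examples are fillers. The next bullet, introduced as a similar case, covers reiterations and rhetorical remarks, and a later one contrasts short questions with substantive ones. On this view the rehabilitation example shows the intended practice, and the OPTIONS section already settles the prompt about options. Coders also reached second-round intraclass correlations of 0.76, 0.83 and 0.87 for Options, Expectations and Risks (SAP, Table 3).

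Much of this stands. The likely intent is content-free utterances, and coders may well have worked that way. It does not remove the conflict in wording. The intraclass correlations argue against a wide split between coders, but they measure agreement: two coders who both took *always* literally would agree while losing the same question.

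A reader might go further and infer that the QPL teaches short questions, so that the loss falls mainly on the intervention arm. In the illustration, a loss of 10% or 20% in that arm only gives:

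- 10%: 0.412 × 0.9 = 0.371, odds ratio (0.371/0.629)/(0.35/0.65) = 1.09
- 20%: 0.412 × 0.8 = 0.329, odds ratio (0.329/0.671)/(0.35/0.65) = 0.91

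The documents do not support that pattern. Coders are blinded to arm. Apart from the prompt about options, every prompt listed in the development paper opens with a sentence of six or more words, and three questions had words added after community feedback. The final brochure figure is not shown, so its exact wording cannot be checked. Brief spontaneous questions could be as common under usual care.

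**Conclusion.** The point holds as a defect in a rule that feeds the primary endpoints. The instruction is inconsistent with a worked example in the same guidance, with the OPTIONS definition and its short examples, and with the OTHER section. Literal use would move brief on-topic questions out of the primary categories.

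The size is unknown and probably modest. Under the assumption of equal loss in both arms, the effect is slight attenuation: 1.30 becomes 1.28 to 1.25 for losses of 10% to 30%. Two stronger readings should not be drawn. The documents do not show that on-topic questions, or the prompt about options, were in fact coded OTHER. Nor do they show a bias specific to the intervention arm. The correction is worth making because it is cheap while coding is blinded, and the same recoding after unblinding would be open to the charge of being post hoc.

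**What to change.** In the manual, limit the rule to stand-alone utterances with no topical content (acknowledgements, echoes, rhetorical fillers). Code all other short questions by content. Replace *always* so that the rule agrees with the repeated-wording example, the OPTIONS section and the OTHER section.

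Before unblinding, check the short questions coded OTHER in both arms under blinded IDs. Use the transcripts as well as the coding sheets: the sheets hold the wording of each question, but the manual does not say that they record whether it stood alone on its line. Check short stand-alone questions coded to a topic in the same pass, so that the review does not run in one direction only. Correct any miscoded rows, use the corrected counts in the primary analysis, and report how many rows changed.

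The cost is one revised rule and some coder hours, with no new data. If few rows change, the sponsor will have shown that the wording did no harm.
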